Research question and objectives	
The overall ADVANCE proof-of-concept (POC) question is to test the system for benefit-risk monitoring of vaccines in Europe. This will first be done by using test cases. For this POC feasibility study, the following research question is used: "Has the initial benefit-risk profile in children prior to school-entry booster been maintained after the switch from whole-cell pertussis vaccines to acellular pertussis vaccines"?
 
The objectives of this specific study, which focuses on the incidence rates of safety outcomes of pertussis-containing vaccines, are:
 
 
1. To evaluate participating databases on quality criteria for inclusion in the study
 
2. To feed safety information into the benefit/risk analysis. The safety information required for the analysis is: 
 
To estimate incidence rates of specific events (i.e. injection site reactions, fever, somnolence, persistent crying, irritability, febrile or afebrile seizure/convulsion, hypotonic-hyporesponsive episode, extensive limb swelling) 
 
a) within specific risk windows after each dose of whole-cell pertussis or acellular pertussis vaccines in pre-school children
 
b) in the time period outside the risk windows before and after each dose of whole-cell pertussis or acellular pertussis vaccines in pre-school children
 
c) Over calendar time, to allow for analysis that will focus on sequential monitoring of B/R
 
 
 
 
 

Countries of study	Electronic health care databases (record linkage, surveillance and GP-based databases) currently available in the ADVANCE consortium and eligible are located in Denmark, Spain, Italy, The Netherlands and UK. Short descriptions of databases and their full names will be included in this protocol upon final decisions of inclusions.

## LIST OF ABBREVIATIONS

ADVANCE	Accelerated Development of VAccine beNefit-risk Collaboration in Europe
AEFI	adverse event following immunization
aP	acellular (pertussis vaccine)
ATC	Anatomical Therapeutic Chemical
CDM	common data model
CI	confidence interval
D1, ..., D5	1 st dose, ..., 5 th dose
DTwP	diphtheria tetanus whole-cell pertussis (vaccine)
DT	diphtheria tetanus (vaccine)
EMC	Erasmus Medical Center
HHE	hypotonic-hyporesponsive episode
ICD	International Classification of Diseases
IEC	independent ethics committee
IMI	Innovative Medicines Initiative
IRB	institutional review board
IR	incidence rate
OR	odds ratio
POC	proof-of-concept
REB	research ethics board
RRE	remote research environment
SCCS	self-controlled case series
WHO	World Health Organization
WP	work package (i.e. WP5)
wP	whole-cell (pertussis vaccine)

## DATABASE LIAISONS/CUSTODIANS

Databases will participate upon demonstration of data quality in the quality assessment module (fingerprinting) that will take place prior to start of the POC feasibility study. Custodians of contributing databases will be members of the study team.

## 2. ABSTRACT

Date April 16, 2016	of	Protocol	Abstract:
Title of Study: Testing new approaches to monitoring benefit/risk with pertussis vaccines as test case: Incidence rates of safety outcomes of whole-cell pertussis and acellular pertussis vaccines in pre-school children.			
Study Period: 01 January 1990 – 31 December 2015			
Rationale and Background: The overall ADVANCE proof-of-concept (POC) question is to test the system for benefit-risk monitoring of vaccines in Europe. This will first be done by using test cases. For this POC feasibility study, the following research question is used: "Has the initial benefit-risk profile in children prior to school-entry booster been maintained after the switch from whole-cell pertussis (wP) vaccines to acellular pertussis (aP) vaccines?" This protocol aims to create the safety data for a benefit-risk analysis of aP versus wP vaccines.			
Research Question and Objectives: The objectives of this specific POC feasibility study focusing on the incidence rates of safety outcomes of pertussis vaccines are: 

1. To evaluate participating databases on quality criteria for inclusion in the study (i.e. vaccination data on pertussis vaccine available, at least one of the outcomes available, data access and clearance of protocol possible within timelines of POC feasibility study).

2. To provide safety information for a benefit/risk analysis model. The safety information required for the model is: incidence rates of specific events (i.e. injection site reactions, fever, somnolence, persistent crying, irritability, febrile or afebrile seizure/convulsion, hypotonic-hyporesponsive episode [HHE], extensive limb swelling) in risk and baseline periods. Incidence rates will be estimated within specific risk windows after each dose of wP or aP vaccine in pre-school children and within the periods outside the risk windows (baseline).

3. To provide calendar time specific incidence data as test for methods development in ADVANCE WP4.

			
Study Design: The main study design is a retrospective dynamic cohort study. The study will be conducted utilizing electronic health care data from ADVANCE partners in different countries (i.e., Short descriptions of databases in respective countries and their full names will be included in this protocol upon final decisions of inclusions). In databases that cover the period in which wP was still provided, the incidence rate (IR) ratio for wP versus baseline risk will be calculated using a self-controlled case series (SCCS) design. This IR ratio will be applied to baseline rates for the aP period in databases that do not capture the wP period, to estimate the rate of events during wP in each specific database.			
Population: The study population will comprise all children registered in any of the participating databases during the study period and for whom an adequate start and end of follow-up and date of birth can be defined. Children will be followed from start of the study period, one month after date of birth (i.e. to allow for pre-vaccination time for the SCCS design and to avoid pre-term related or birth-induced increase in incidence rates), or date of valid data in the database (whichever is the latest) until the end of study period (31-12-2015, the school-entry pertussis booster, transferring out of the database, death, reaching age 6 years: whichever is the earliest).			

**Variables:***Exposure of interest*

Any wP vaccines and aP pertussis-containing vaccines and their doses in the vaccine schedule (D1, D2, D3, D4, D5)

*Outcomes*

- Injection site reactions: erythema, edema, induration/nodule/sterile abscess, pain/tenderness
- Fever
- Somnolence
- Persistent crying, irritability
- Generalized convulsive seizures
- HHE
- Extensive limb swelling

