#### **7.2.5. Population Selection**

The study population will comprise all children registered in any of the participating databases during the study period and for whom an adequate start and end of follow-up and date of birth can be defined. Children will be followed from start of the study period, one month after date of birth (i.e. to allow for pre-vaccination time for the SCCS design and to avoid pre-term related or birth-induced increase in incidence rates), or date of valid data in the database (whichever is the latest) until the end of study period (31-12-2015, the school-entry pertussis booster, transferring out of the database, death, reaching age 6 years: whichever is the earliest). Persons with missing dates of birth or sex will not be included.

For the incidence rate part of the study, we will retain all subjects meeting age and calendar time inclusion criteria with person time greater than zero.

The vaccination day and outcome-specific risk-windows after vaccination will be classified as risk periods, and the period between the end of the risk-window after vaccination until the next pertussis-containing vaccination or end of follow-up as the baseline period. To keep track of dose these periods will also be labeled by the number of previous pertussis-containing vaccinations. For all eligible subjects, CohortStart will be equal to PopulationStart and CohortEnd equal to PopulationEnd.

Databases will be asked to provide dates during which both wP and aP pertussis vaccines were both being used in the population. Patient time during the period of the switch from wP to aP will be removed from the cohort and SCCS analyses to avoid misclassification of exposures.

In order to avoid confounding by infections or other vaccinations, the study population for the incidence rate cohort design will NOT be the same as for the SCCS design.

For the self-controlled case series, analysis sets containing cases of each of the outcomes under study will be defined. For each of these cases, exposure will be defined as: exposed to wP and exposed to aP.

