The study population for each outcome-specific SCCS analysis will be those subjects who experienced the event at least once during follow-up. Eligible person time for these subjects will be one month before the first recorded pertussis vaccine exposure until one month after the last pertussis vaccine exposure. Risk periods will be those specified for each outcome after each dose. Baseline periods will be days -31 to -8 before exposure and the interval from the last day of the risk window + 1 to day 31.

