##### **7.2.8.2. Analysis of Demographics and Baseline Characteristics**

The population of subjects meeting the study population (i.e. cohort) inclusion criteria will be described in terms of the following variables. Continuous variables will be described as means, medians (i.e. follow-up time) and standard deviations, while categorical variables will be described as frequencies and percentages:

- age and sex at study population (i.e. cohort) entry, age at D1, D2, D3, D4, D5 by country, follow-up time in the cohort by calendar year and month, dose and age (year of birth), number of pertussis vaccine doses per child.

---

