### 7.2.8.3. Statistical Methods

#### COHORT STUDY

The incidence rate of each event will be calculated using a dynamic cohort approach. For each person in the cohort, follow-up time will be classified by calendar year, sex, age in year of birth and months and the different risk window (see exposure section). This persontime will be the denominator for the incidence rate calculations. Incidence rates will be calculated stratified by:

1. type of vaccine: wP/aP
2. database, country
2. dose of wP/aP (actually received dose)
3. risk window
4. age in months and year of birth
5. calendar year

[figure not shown]
Cases will be counted in the numerator for the rate calculation if the date of onset/occurrence of an event falls into the specific window of that vaccine, and will be further stratified to count in the correct age/sex and calendar year category at the date of onset.

A Poisson distribution will be used to calculate 95% CIs.

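### The school-entry booster ends follow-up yet falls within the listed exposures D1 to D5, so that dose (D4 or D5) has no valid cohort rate or SCCS ratio under the rules as written

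*Protocol*

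**What the plan says.** All references are to the Protocol.

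- **End of follow-up.** Section 7.2.5 (also the Abstract and the text under Figure 1) stops follow-up at the earliest of the study end date and "the school-entry pertussis booster, transferring out of the database, death, reaching age 6 years: whichever is the earliest". Section 7.2.4 bounds the source population in the same way, and the research question in section 6 concerns children before that booster.
- **Doses.** The Abstract lists as exposure "Any wP vaccines and aP pertussis-containing vaccines and their doses in the vaccine schedule (D1, D2, D3, D4, D5"). Section 7.2.8.2 describes "age at D1, D2, D3, D4, D5 by country". Section 7.2.8.3 (Cohort study) stratifies rates by "dose of wP/aP (actually received dose").
- **SCCS cases.** Section 7.2.5 takes "those subjects who experienced the event at least once during follow-up".
- **SCCS person time.** The next sentence sets it as "one month before the first recorded pertussis vaccine exposure until one month after the last pertussis vaccine exposure". No cut at end of follow-up is stated, and section 7.2.8.3 (SCCS) enters every available pertussis dose as an exposure.
- **Day 0.** Sections 7.2.7.1 and 7.2.9 count the vaccination day as risk time.

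**The concern.** The dose to be studied is also the event that censors the child. A risk window that opens on the last day of follow-up cannot supply a risk-window rate, so the dose list and the follow-up rule disagree about the last scheduled dose.

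The SCCS adds a second conflict. Case selection looks only at events up to the booster, while person time, as worded, can run a month beyond it. A child whose only event follows the booster is then not a case, yet children with an earlier event contribute post-booster time. Inclusion depends on events in one part of the observation period and not in the other, and that biases the estimate for the excluded part.

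The transformation scripts are common to all databases, so an unclear censoring rule would be coded everywhere. The rates and SCCS ratios feed the benefit-risk model (section 7.3.1), and the wP ratios are multiplied into baseline rates of databases without wP data (section 7.2.1). An invalid dose-specific figure would be carried forward.

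**Working it through.** The protocol gives no figure on this point to reproduce.

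**1. Which dose is the school-entry booster?** Dose number = primary doses + toddler booster + 1, using the schedules in section 5 (text under Figure 1, Figure 2 and the text after it).

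- 2+1: 2 + 1 + 1 = D4
- 3+1: 3 + 1 + 1 = D5
- Three primary doses, no toddler booster (two countries, according to section 5): 3 + 0 + 1 = D4

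**2. How much of its risk window lies in follow-up?** Windows are from section 7.2.7.1, counted in whole days from day 0. The protocol does not say whether the end date is included. If it is excluded, the answer is 0 days for every outcome. If it is included, only day 0 remains:

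| Outcome | Window | Risk days | Share observed |
|---|---|---|---|
| Injection site reactions, extensive limb swelling | 0-7 days | 8 | 1/8 = 12.5% |
| Fever, generalized convulsions | 0-72 h | 4 | 1/4 = 25% |
| Somnolence, HHE | 0-48 h | 3 | 1/3 = 33% |
| Persistent crying, irritability | 0-24 h | 2 | 1/2 = 50% |

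**3. SCCS, literal reading.** Let m be the mean number of pre-booster events per child. It is not in the documents, so a range is shown. With Poisson events at a constant rate, a child is included with probability 1 − exp(−m). That is also the share of booster-period events captured:

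| m | Share captured |
|---|---|
| 0.001 | 0.1% |
| 0.02 | 2.0% |
| 0.1 | 9.5% |
| 0.5 | 39% |
| 1.0 | 63% |

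If only first events count, the share is zero.

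*Example (assumed inputs).* Four earlier doses plus the booster; 4 risk days per dose; baseline of 24 days before (days −31 to −8) and 28 days after (days 4 to 31) each dose; no overlap; true ratio 3; inclusion probability 0.0201.

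- Baseline days: 5 × (24 + 28) = 260, of which 28 follow the booster.
- Observed baseline rate relative to the true rate: (232 + 28 × 0.0201)/260 = 0.8945.
- Booster ratio without age adjustment: 3 × 0.0201/0.8945 ≈ 0.07.
- Booster ratio within its own age stratum, so that only its own 52 baseline days serve as reference: 3 × 0.0201 × 52/(24 + 28 × 0.0201) ≈ 0.13.

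With or without an age term, a true ratio of 3 appears as strong protection.

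**4. SCCS, nested reading.** If person time stops at end of follow-up, the selection problem disappears. The booster then has 0 risk days, or day 0 only, as in step 2.

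Neither reading gives a valid booster-dose estimate.

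**The case against.** **The SCCS bias depends on the reading.** The SCCS sentences stand in the section that has just ended follow-up at the booster, and the source population stops there too. A nested reading is natural, and under it no booster time is gained. This stands: the bias is certain only under the literal wording. But the text does not choose, and the nested reading also leaves the booster without a usable window. The statement in section 7.2.5 that the cohort and SCCS populations differ does not settle it, because the reason given there is confounding by infections or other vaccinations.

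**A reader might infer that the ratios of the earlier doses are inflated too.** In the example above they come out at 3/0.8945 = 3.35 instead of 3, about 12% too high, because post-booster baseline days are almost empty. That assumes no age adjustment. Section 7.2.8.3 puts age in days and season in the model. With assumed doses at 2, 3, 4 and 11 months and 4 years, the unadjusted earlier-dose ratio is 3.45. One term separating infancy from age 4 returns it to 3.00, because the event-poor time lies at its own age. The planned model therefore does not support a material inflation.

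**A reader might infer that D5 is out of reach in every eligible country throughout.** Figure 2 shows schedules as of October 2015, whereas the study covers 1990 to 2015 and section 5 says that countries added, removed and moved doses. An extra off-schedule dose before the booster could also be labelled D4 or D5. The affected dose number may vary by country and year, so the claim is limited to the on-schedule school-entry booster.

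**A reader might infer that a D5 rate is promised outright.** Table 6 shows only Doses 1 to 3 and notes that the number depends on country and year, and section 7.2.8.1 aggregates strata with zero events. That softens the promise. It does not reconcile the exposure list and the stratification by received dose with the follow-up rule.

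**Conclusion.** The contradiction is real and lies within the protocol. An on-schedule school-entry booster is listed as an exposure but ends follow-up. Its cohort risk window holds 0 days or day 0 only (12.5% to 50% of the window, depending on the outcome), so its rate cannot be validly estimated. In the SCCS its ratio is either biased towards zero (literal reading) or has no usable window (nested reading).

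The capture shares rest on a constant event rate and an assumed m. The example ratios of 0.07 and 0.13 also rest on an assumed true ratio of 3. They show the direction and possible size of the bias and are not forecasts. Earlier-dose ratios are expected to change little once age is modelled. Age at D4 or D5 can still be described, since the date of the booster is known. The research question does not need a booster-dose estimate, so this is a point that should be corrected and does not threaten the study's main purpose.

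**What to change.** Reconcile the Abstract (Variables), section 7.2.5 and section 7.2.8.3 in one of two ways.

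1. **Closest to the research question.** End follow-up and SCCS person time before the day of the school-entry booster, and say so explicitly. Exclude that booster, whatever its dose number, from the doses for which risk-window rates and SCCS ratios are estimated. Define it by its place in the local schedule for the country and calendar year, since a fixed dose number will not serve.
2. **Alternative.** If a booster-dose estimate is wanted, extend follow-up past the booster for both case selection and person time, far enough to cover the risk window and the post-dose baseline to day 31.

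Under either option, age at D4 and D5 in section 7.2.8.2 can stay as a descriptive item.

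The cost is protocol wording and conditions in the common scripts. Option 1 gives up a booster-dose rate that the research question does not ask for. Option 2 takes the study beyond its stated pre-booster scope.

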**Data Sources:**

- Electronic health care databases (record linkage, surveillance and GP-based databases) currently available in the ADVANCE consortium and eligible are located in Denmark, Spain, Italy, The Netherlands and UK. Short descriptions of databases and their full names will be included in this protocol upon final decisions of inclusions.

**Study Size:** Total population (0-6 year of age) of all eligible ADVANCE databases

**Data Analysis:** The purpose of this study is to provide incidence rates (i.e. baseline and risk-window specific) of known adverse reactions following vaccination with pertussis-containing vaccines for use in a multi-criteria decision analysis (MCDA) model of benefits and risks of wP versus aP pertussis vaccines (models are described in a separate benefit-risk study protocol). In some more recent databases, wP information will not be captured. To generate risk-window specific incidence rates for the wP period in these databases, the IR ratio originating from an SCCS analysis of wP versus baseline in other databases will be multiplied by the baseline IR.

**Informed Consent and Ethical Approval:** This study will be conducted on the basis of secondary use of electronic healthcare records. Each database will apply local governance and privacy rules prior to aggregating and sharing anonymized data.

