### **TYPE OF PERTUSSIS VACCINES**

Vaccines against pertussis were developed in the 1920s and have been used more widely since the 1940s [7]. The first vaccines were wP vaccines containing suspensions of killed *B. pertussis* organisms [4]. The production process varied between different wP vaccines, resulting in differences in antibody responses. Furthermore, due to the use of the whole bacterium, composition and thus immunogenicity, efficacy and reactogenicity of a specific wP vaccine could change over time, from lot to lot within one wP vaccine, and from one wP vaccine to another. Reactogenicity of the wP vaccine is probably due to their endotoxin lipopolysaccharide (LPS) content [8]. In an attempt to reduce reactogenicity, aP vaccines were developed. They were used for the first time in 1981 during mass vaccination campaigns in Japan [9], and more widely during and since the 1990s. aP vaccines contain purified secreted and surface components of *B. pertussis* which, based on animal models, are thought to play an important role in pathogenesis and induction of immunity [4]. Later on, several aP vaccines were manufactured, containing between one and five different pertussis components [2].

All aP vaccines contain at least a detoxified pertussis toxin (PT); the second antigen added in all formulations with two or more components is filamentous haemagglutinin (FHA); three-component vaccines contain also pertactin (PRN); finally, four- and five-component vaccines contain one or more fimbrial agglutinogens or fimbriae (FIM). Almost all aP vaccines are adjuvanted with aluminium salts and combined with diphtheria and tetanus toxoids, and possibly also additional vaccine valences such as inactivated poliovirus, *Haemophilus influenzae* type b and/or hepatitis B [4].

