## **7.2. Methods for estimations in the scientific question**

### **7.2.1. Design**

This is a retrospective dynamic cohort study to estimate incidence rates of safety outcomes.

A SCCS design will be used to estimate IR ratios for wP vaccines versus baseline periods in databases that capture data on wP vaccinations and will be applied to databases that do not capture data on wP vaccinations to estimate IR in risk windows for those databases.

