#### OPERATIONALIZATION

Vaccinations will be obtained from the databases by using names of vaccines and database specific codes. Vaccines will be categorized as wP, aP or unknown. There will be no further stratification in brand or product name (see Appendix 4 for categorization).

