### 7.2.9. Limitations

In this POC feasibility study that tests and evaluates the ADVANCE system, tailored to generate rapid evidence on vaccine effects, there are several methodological limitations. These limitations will be assessed, and are an integral part of the system evaluation process. The following points are considered to be the expected limitations:

- Given that this POC feasibility study evaluates a system and its different processes, the epidemiological results produced (i.e. incidence rates and risk ratios) should not be considered as evidence that can be directly translated to inform epidemiological and pharmacovigilance decision-making processes. The epidemiological results produced in this POC feasibility study are part of a set of evaluation indicators to test the ADVANCE system and may not be the best or true estimates
- It could be possible that within the process of database selection it will become evident that proposed case definition(s) for the events are either different, or are differently interpreted, in a specific database or country. Different countries and databases could be using different case definitions. To address this limitation, the study will produce country-and database-specific analyses and results.
- Some event outcomes are signs and symptoms and not disease entities. The coding in databases might not be applicable to signs and symptoms (e.g. crying). Therefore, database extraction algorithms and strategies need to be adapted (e.g. include also free text search).
- Event codes in databases might contain the whole spectrum of potential, probable and confirmed cases. Given the POC feasibility study nature to test the system and to save costs and time, diagnostic codes will not be validated on a patient level using medical histories and charts.

- 
- It is expected that only a limited number of databases will have information on wP vaccination available. Therefore, the suggested strategies in the methods sections 7.4.3 (i.e. multiplying baseline incidence rates with IR ratios across databases, time periods, and wP/ aP data) will be applied. The additional use of literature information will be carefully evaluated and interpreted.
  - The type of database used (e.g. GP database, hospital database, claim database, etc) will influence incidence rates. To address this limitation, the study will produce country/ database-specific analyses and results.

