  - The current methodology will not account for differences in vaccination schedules: different countries use different vaccines and schedules that may have changed over time. ATC codes will be used to identify which types of vaccines were used; this will allow stratification on vaccine types. Further, risks on schedule level will not be evaluated but will be evaluated on a dose level as each case is followed after each dose given.
  - Misclassification or missing information on vaccinations and events is a common limitation of observational studies conducted in electronic healthcare databases. Missingness and misclassification will be carefully followed and attempts will be made to implement data cleaning procedures (e.g. probability of wP or aP vaccine given the time of administration, dose according to timing in vaccination schedule, etc). Records with missing dates (i.e. birthdates, data of vaccination, date of event occurring) will be excluded. ATC code is a mandatory data field. A missing dose information will be derived (i.e., dose will be per recommendation, as determined by the database custodian based on knowledge of the local immunization schedule and as documented in an analytic variable generated for the purpose of the study).
  - aP and wP vaccine administration could have been overlapping. The period of potential overlap in a database will be excluded if aP or wP vaccine type information is missing (i.e. database entry is only referring to 'pertussis vaccine' and aP or wP is not specified).
  - The smallest possible time unit in electronic healthcare databases is 'days'. This could potentially make it difficult to judge whether vaccination happened before the event or vice versa when recorded on the same day. In this study, it is assumed a priori that vaccination occurs before the event whenever they are recorded on the same day, so the vaccination day is classified as risk period and starting at Day 0.

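### Derived wP rates assume the same wP-versus-baseline ratio across wP products and databases, against the protocol's own account of wP vaccines

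*Protocol*

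**What the plan says.** The rule appears in four places of the protocol.

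- Abstract, Study Design: "This IR ratio will be applied to baseline rates for the aP period in databases that do not capture the wP period". The stated aim is a wP event rate for every receiving database individually.
- Abstract, Data Analysis: "the IR ratio originating from an SCCS analysis of wP versus baseline in other databases will be multiplied by the baseline IR".
- Section 7.2.1: SCCS ratios from databases with wP data "will be applied to databases that do not capture data on wP vaccinations to estimate IR in risk windows for those databases".
- Section 7.2.9: cross-database multiplication is named as the strategy to use because few databases are expected to hold wP data.

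None of these places sets a condition on the donor's wP product, country or type of care, and none says that the ratio is assumed constant.

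The protocol also describes the vaccines and the data:

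- Section 5, Type of Pertussis Vaccines: "reactogenicity of a specific wP vaccine could change over time, from lot to lot within one wP vaccine, and from one wP vaccine to another".
- Section 7.2.9, on countries: "different countries use different vaccines and schedules that may have changed over time".
- Section 7.2.7.1, Operationalization, sorts vaccines into wP, aP or unknown. It adds: "There will be no further stratification in brand or product name".
- Section 7.2.9, on data sources: "The type of database used (e.g. GP database, hospital database, claim database, etc) will influence incidence rates". The remedy offered is that "the study will produce country/ database-specific analyses and results".

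**The concern.** The benefit-risk question is whether the profile held after a country switched from its wP vaccine to an aP vaccine. In a database with no wP data, the wP side of that comparison is the local baseline multiplied by a ratio measured elsewhere, possibly on another wP product. Section 5 gives a reason to expect that ratio to differ between products, and the exposure definition removes the means of seeing the difference. Section 5, Vaccine Risks, even speaks of the wP vaccine used in the Netherlands as a national product.

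The promise of database-specific results does not solve this. In a receiving database only the baseline factor is local.

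Section 7.3.1 (Table 6) feeds these rates by country into the benefit-risk model. A reader of that table could not tell an observed wP rate from a derived one. The derived rate could also look more precise than it is, if its interval reflects only the sampling error of the SCCS estimate.

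**Working it through.** The protocol gives no numerical transported rate, power or sample size, so there is no figure to reproduce. The check is the algebra of the rule, followed by a test of whether the protocol's own figures can size the error.

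**1. Propagation.** Let D be the donor database, R the receiver, and IRR the wP-versus-baseline ratio.

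- Derived rate = baseline IR(R) × IRR(D)
- Rate wanted = baseline IR(R) × IRR(R)
- Error factor = IRR(D) / IRR(R)

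The local baseline cancels, so the whole difference in ratios enters the derived rate. If IRR(R) is 4 (assumed), a donor ratio of 8 doubles the derived rate (8/4 = 2) and a donor ratio of 2 halves it (2/4 = 0.5). IRR(R) cannot be observed in a database without wP data, so the receiver cannot detect the error.

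**2. Care setting.** Let c1 and c0 be the probabilities that an event is captured in the risk and baseline windows. Then observed IRR = true IRR × c1/c0. With a true IRR of 4 (assumed):

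| c1 | c0 | observed IRR |
|---|---|---|
| 0.2 | 0.2 | 4 |
| 0.4 | 0.2 | 8 |
| 0.1 | 0.2 | 2 |

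A setting that lowers capture equally in both windows leaves the ratio unchanged. Setting biases the transfer only if c1/c0 differs between donor and receiver.

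**3. Interval.** Let τ be the between-database SD of log IRR and se the SCCS standard error of log IRR. Assume one donor, donor and receiver drawn independently, and the local baseline known.

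- SD of the error on the log scale: s = √(2τ² + se²)
- Coverage of an interval using se alone: 2Φ(1.96·se/s) − 1
- Example, τ = 0.3 and se = 0.2: s = √(0.18 + 0.04) = 0.469; 1.96 × 0.2/0.469 = 0.836; coverage 0.597

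| τ (assumed) | se 0.1 | se 0.2 | se 0.3 |
|---|---|---|---|
| 0.1 | 74% | 89% | 92% |
| 0.3 | 35% | 60% | 74% |
| 0.5 | 22% | 41% | 56% |

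For a given τ, coverage is worse when the SCCS estimate is more precise.

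**4. Can the protocol supply the size?** Section 5, Vaccine Risks, allows two comparisons.

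- wP frequencies in the two US studies: pain 50.9/27.3 = 1.86; fever 46.5/27.3 = 1.70; redness 49.4/37.4 = 1.32; swelling 40.7/39.7 = 1.03. Pain is higher in one study and redness in the other. The fever thresholds differ (38 °C and 37.8 °C). The 27.3% is after the first dose, while the other study reports over 15,752 doses.
- wP/aP ratios, trial-based source against Dutch questionnaire study: crying 7 against 1.5/0.4 = 3.75 (factor 1.87); fever of at least 40.5 °C 7 against 0.8/0.2 = 4.0 (1.75); HHE 17 against 0.12/0.03 = 4.0 (4.25); seizures 6 against 0.06/0.02 = 3.0 (2.0). The Dutch figures are dose-specific and come from questionnaires, and the denominator is aP, not baseline.

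Neither set isolates product or measures a wP-versus-baseline ratio. They show that sources disagree, but give no estimate of τ or of the error factor.

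**The case against.** The strongest reply has four parts.

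**The protocol states no pooled ratio.** A reader might infer from the singular wording that one common ratio is exported everywhere. The text does not say so. It does not say how donors are chosen or combined, Figure 4 is not shown, and the analysis plan may settle both. This stands, and the point does not rest on pooling: a ratio from a single donor carries the same assumption. What the protocol itself fixes is the unconditional transfer and the exclusion of product.

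**Database type concerns rates, not ratios.** A reader might infer that applying a GP-based ratio to an inpatient-only source such as IT_ASLCR in Table 4 is wrong in itself. The documents do not support that. The receiver's own baseline is used, so an equal effect cancels (step 2), and Table 4 lists only potential databases still subject to fingerprinting. Differential capture is plausible for fever, crying or local reactions, but it is not shown.

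**Product data may be thin.** The brand item in Table 5 measures how far records reach brand level, and Appendix 1 expects mainly vaccine type and ATC code. Per-product ratios will often be impossible, and variation by lot and over time remains even in directly observed wP rates. This limits the remedy but does not remove the assumption.

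**The protocol disclaims its results.** Section 7.2.9 warns that the estimates may fall short of the true values and are not for direct use in decisions, and section 8.1 calls the aims methodological. This lowers the stakes. It is general, however: it neither names the constancy assumption nor identifies the affected cells, and the rates still enter the benefit-risk model.

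**Conclusion.** The point holds for product and database constancy. The rule treats the wP ratio as transferable without condition, while the protocol itself reports variation between wP products and over time and different vaccines between countries, and bars stratification by product. The error passes one-for-one into the derived wP rate, its direction is unknown, and it cannot be seen in the receiving database. An interval built on the SCCS standard error alone would be too narrow whenever the true ratios differ between databases. The coverage figures in step 3 depend on assumed values of τ and se.

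The size cannot be estimated from this protocol. A reader might take the 1.3- to 2-fold differences between studies in Vaccine Risks as a product effect; dose, threshold and ascertainment also differ, and swelling hardly differs at all. Nor do the documents show that a derived rate will describe a vaccine never used in the receiving country. Donors are not yet fixed, so this is only a possibility. Care setting is a secondary, conditional issue.

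The change should be made before analysis. It does not invalidate the study.

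**What to change.** In sections 7.2.1 and 7.2.8.3:

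1. State the assumption that the wP-versus-baseline ratio is constant across wP products and databases.
2. Estimate the ratio separately in each donor database, and per wP product where brand is recorded, as a stated exception to section 7.2.7.1.
3. Compute the derived wP rate under each donor. Show the range across donors, or carry between-donor variance into the confidence interval.
4. Where only one donor exists, state that the derived rate is conditional on that donor's product.
5. Where donor and receiver differ in type of care, flag it, or add a sensitivity analysis restricted to donors of the same setting. Mandatory empty cells are not needed: few donors are expected, and the benefit-risk model needs wP inputs.

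In Table 6 (section 7.3.1), mark derived wP cells as derived and name the donor database, its type of care and its wP product where known.

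The cost is rerunning an existing model per donor, with no new data collection, plus extra table columns and wider wP intervals. With very few donors, between-donor variance will be poorly estimated, and the donor-by-donor range is then the more candid display.
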